9.1. Adverse Events

The following adverse event tables will be displayed:

- Overall summary of TEAEs, to include total number of TEAE, frequency of subjects with TEAEs, drug-related TEAEs, SAEs, drug-related SAEs, Grade 3 or higher TEAEs, drug-related Grade 3 or higher TEAE, or death within 30-days within administration of study-drug, and AEs leading to permanent discontinuation of study drug
- Overall summary of exposure-adjusted TEAE incident rates, calculated as number of events per cycle, and corresponding 95% confidence intervals frequency and percentage of TEAEs by SOC and preferred term (PT)
- Frequency and percentage of TEAEs by SOC/PT by maximum CTCAE toxicity grade
- Frequency and percentage of hematology-related TEAEs by SOC and PT
- Frequency and percentage of hematology-related TEAEs by SOC/PT by maximum CTCAE toxicity grade
- Frequency and percentage of chemistry-related TEAEs by SOC and PT
- Frequency and percentage of chemistry-related TEAEs by SOC/PT by maximum CTCAE toxicity grade
- Frequency and percentage of renal-related TEAEs by SOC and PT

- Frequency and percentage of renal-related TEAEs by SOC/PT by maximum CTCAE toxicity grade
- Frequency and percentage of Grade 3 or 4 toxicities with PT of Fatigue
- Frequency and percentage of Grade 3 or 4 toxicities with SOC of Gastrointestinal Disorders
- Median duration in days for all TEAEs by SOC/PT
- Frequency and percentage of study-drug related TEAEs by SOC/PT
- Frequency and percentage of Grade 3 or higher study-drug related TEAEs by SOC/PT
- Frequency and percentage of SAEs by SOC/PT
- Frequency and percentage of study-drug related SAEs by SOC/PT
- Frequency and percentage of TEAEs leading to permanent discontinuation of study drug

Per subject listing of AE information will be provided. Per subject detailed information of SAE, Death on Study, and AEs that lead to study discontinuation will also be provided in separate listings.

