10.9 Adverse Event Reporting Period

The adverse event reporting period for safety surveillance begins when the subject is included into the trial (date of first signature of informed consent) and continues through the trial’s post-treatment follow-up period, defined as 30 days from the final administration of the trial treatment or immediately before initiation of any other anticancer therapy, whichever comes first.

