Based on the high antitumor activity observed in AITL subjects in the AITL cohort and other portions of the study, enrolment in the AITL cohort has been expanded to include up to 20 additional subjects with tumors of AITL and related T follicular helper cell histologies in order to further characterize the safety and tolerability of tipifarnib in this relatively rare population. The selection of 20 subjects was empirical and no statistical hypotheses will be tested. Descriptive statistics will be used to report response rate.

Eligible subjects will receive tipifarnib administered at a starting dose of 300 mg, orally with food, BID on days 1 - 21 in 28-day cycles. Stepwise 100 mg dose reductions to control treatment-related, treatment-emergent toxicities are allowed and further detailed in Section 9.5. Subjects who received tipifarnib bid on Days 1 – 7 and Days 15 – 21 in 28-day cycles during the conduct of earlier versions of this protocol may remain on that dose regimen at the discretion of the investigator. Alternatively, the subject may transition to receive a dose of 300 mg, orally with food, bid on Days 1-21 of 28-day treatment cycles beginning on Day 1 of their next cycle.

Subjects may use proton pump inhibitors or H2 antagonists during the treatment portion of this study. However, subjects should be instructed to use antacids (magnesium or aluminum containing products) at least 2 hours before or after intake of oral study drug.

In the absence of emerging unmanageable toxicity, subjects may continue tipifarnib treatment for as long as the investigator considers that the treatment is providing clinical benefit up to 12 months since the subject's enrollment. Treatment may continue beyond 12 months upon agreement by the Investigator and Sponsor if there is documented evidence of sustained clinical benefit.

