7. SUMMARY OF STUDY POPULATION DATA

7.1. Subject Disposition

Subject disposition will be provided for all subjects screened. The disposition table will include the total number of subjects screened, total number of screen failures, and total number who received any study drug will be displayed. Among subjects who received any study drug, frequency and percentage of subjects who completed treatment, prematurely discontinued and reasons for premature discontinuation and reason for end of study will be tabulated. Subjects will be presented throughout by their genetic subtype: AITL, PTCL, CXCL12+, and an Other category, which includes one subject that is ALCL-ALK negative and one that is PTCL sub-type not otherwise specified in the protocol.

Detailed subject disposition information, subject eligibility, and analysis population assignment will be displayed in separate listings.

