7.4. Dosing and Extent of Exposure

Number of treatment cycles and average dose intensity per treatment cycle will be summarized using descriptive statistics. Total incidences of drug modification (dose reduction, dose interruption, dose increase, or drug withdrawn), frequency and percentage of subjects who experienced drug modification, and summary statistics of number of drug modifications per subject will also be summarized.

Per subject log of study drug number of pills returned and dispensed will be displayed in a listing; tipifarnib dosing log will also be displayed in a listing.

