9. SAFETY ANALYSIS

Safety and tolerability of tipifarnib will be assessed based on the following:

- Incidence, duration and severity of treatment-emergent adverse events, serious adverse events, adverse events resulting in permanent discontinuation of study drug, and deaths within approximately 30 days from the last dose of study drug (or immediately before the administration of another anti-cancer treatment)
- Laboratory test results
 - Serum Chemistry: Blood Urea Nitrogen (or Uric Acid), Creatinine, Sodium, Potassium, Calcium, Total Protein, Albumin, Total Bilirubin, Alkaline Phosphatase, ALT/SGOT, AST/SGPT, Lactate Dehydrogenase;
 - Hematology: White Blood Cell Count, Hemoglobin, Platelet Count, Neutrophils, Lymphocytes, Monocytes;
 - Coagulation Panel: Prothrombin Time and International Normalized Ratio (PT/INR), Activated Partial Thromboplastin Time (APTT);
- Changes in vital signs including blood pressure, pulse, and temperature;
- Changes in electrocardiogram results.

Adverse events will be coded using MedDRA per the Data Coding Plan. Treatment-emergent adverse events are defined as adverse events that start on or after the first dose of study drug and within 30 days of the last administration of study drug or immediately before the initiation of any other anticancer therapy. Adverse events will be summarized by the number and percentage of subjects who experienced the event, according to system organ class and preferred term. A subject reporting multiple cases of the same adverse event will be counted once within each system organ class and similarly counted once within each preferred term.

Unless specified otherwise, the denominator for these calculations will be based on the number of subjects who received at least one administration of tipifarnib regardless of the total number of doses or treatment cycles administered. These conventions will be appropriately modified to calculate AE incidence rates separately for each cycle that study therapy is administered. AE incidence rates may also be calculated based on other measures of subject exposure (e.g., total number of treatment cycles administered).

AE durations will be calculated using all TEAEs. For AEs that are still ongoing at the end of study, we will use the last contact date as the end of AE stop date for calculating the duration of AEs. Median, minimum and maximum of AE durations will be reported.

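### The exposure-adjusted TEAE rate counts events beyond the last cycle but divides by cycles, so it depends on how long subjects were treated

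*SAP*

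**What the plan says.** The SAP lists, among its adverse event tables (9.1), an "Overall summary of exposure-adjusted TEAE incident rates, calculated as number of events per cycle", with 95% confidence intervals. SAP 9 gives the only hint of what the cycle count is: "AE incidence rates may also be calculated based on other measures of subject exposure (e.g., total number of treatment cycles administered").

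The events that enter the rate are TEAEs. SAP 9 defines these as events starting on or after the first dose and "within 30 days of the last administration of study drug or immediately before the initiation of any other anticancer therapy". Protocol 10.9 sets the same limit on AE collection: "defined as 30 days from the final administration of the trial treatment or immediately before initiation of any other anticancer therapy, whichever comes first".

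Dosing is "BID on days 1 - 21 in 28-day cycles" (SAP 3.1), so the rest week lies inside the cycle. For exposure, SAP 7.4 summarises "Number of treatment cycles and average dose intensity per treatment cycle"; it does not mention time at risk. SAP 7.1 adds: "Subjects will be presented throughout by their genetic subtype: AITL, PTCL, CXCL12+, and an Other category".

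Neither document restricts the numerator of this rate to events within cycles, adds the follow-up days to the denominator, or says how a partly given or delayed cycle is counted.

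**The concern.** An exposure-adjusted rate is useful when subjects are treated for different lengths of time. It can only do that job if events and exposure are counted over the same period. Here the event window usually outlasts the last cycle, by a number of days that does not grow with time on treatment. That fixed excess is large relative to one or two cycles and small relative to twelve. Two groups with the same daily AE rate would then show different events per cycle merely because one was treated longer.

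Tolerability is a stated purpose of part of this trial: up to 20 subjects with AITL and related histologies were added to characterise safety further (Protocol 12.4, SAP 3.1). SAP 7.1 also presents results by subtype, so a reader is likely to compare this rate across groups. The confidence intervals planned for it carry the same mismatch.

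**Working it through.** The documents give no AE rate or person-time for this item, so there is no figure of theirs to reproduce. The check is person-time arithmetic.

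**Inputs from the documents**
- Cycle length 28 days, last scheduled dosing day 21 (SAP 3.1).
- Event window: 30 days after last dose, shortened by other anticancer therapy (SAP 9).
- Denominator: number of cycles (SAP 9.1).

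**Inputs the documents do not give, taken as assumptions**
- h, the AE rate after the end of the last cycle relative to the rate before it: 0 to 1.
- Days from last dose to other anticancer therapy: 7 to 30.
- A cycle once started counts as one.

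**Formula.** For c cycles, last dose on day d of the last cycle, and w days of follow-up, the event window is 28(c − 1) + d + w days and the denominator stands for 28c days. At a constant AE rate, events per cycle are multiplied by

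[28(c − 1) + d + w] / (28c).

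**Full window, last dose on Day 21.** With d = 21 and w = 30 the window is 28c + 23 days. The excess is 23 days, not 30, because 7 rest days are already in the cycle. With a lower rate in the excess days the factor is 1 + 23h/(28c).

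| Cycles | h = 1 | h = 0.5 | h = 0 |
|---|---|---|---|
| 1 | 51/28 = 1.82 | 1.41 | 1.00 |
| 2 | 79/56 = 1.41 | 1.21 | 1.00 |
| 3 | 107/84 = 1.27 | 1.14 | 1.00 |
| 5 | 163/140 = 1.16 | 1.08 | 1.00 |
| 12 | 359/336 = 1.07 | 1.03 | 1.00 |

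**Earlier last dose, full window, 1 cycle, h = 1.** Day 14: 44/28 = 1.57. Day 7: 37/28 = 1.32. Day 1: 31/28 = 1.11. With the full 30 days the factor always exceeds 1 when h = 1.

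**Window cut by other therapy.** The factor is 1 when d + w = 28 and falls below 1 when d + w is smaller.
- Last dose Day 21, therapy 14 days later: 35/28 = 1.25 (1 cycle), 63/56 = 1.125 (2), 147/140 = 1.05 (5).
- Last dose Day 21, therapy 7 days later: 1.00 for any number of cycles.
- Last dose Day 10, therapy 7 days later, partial cycle counted as whole: 17/28 = 0.61 (1 cycle), 45/56 = 0.80 (2), 325/336 = 0.97 (12).

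**Delayed cycles.** The SAP does not say how these count. If a cycle stretched by 14 days counts as one and the AE rate is unchanged during the delay, the factor for that cycle is 42/28 = 1.5.

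**With time at risk as the denominator.** Take one event per 28 days. One cycle with the full window gives 51/28 = 1.82 expected events over 51/28 units of 28 days, a rate of 1.00. The result is 1.00 for every number of cycles, because both parts of the rate cover the same days.

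**The case against.** The strongest objection is that neither direction nor size is settled. Subjects with few cycles may be those who progress and switch therapy early, and their factor can be 1.00 or lower. For example, a 2-cycle group switching 7 days after a Day 21 last dose (1.00) would look better than a 5-cycle group with the full window (1.16): 1.00/1.16 = 0.86. The AE rate after stopping is unknown, and Protocol 5.1.2 says that enzyme inhibition reverses within 3 to 7 days. This stands, and it limits what can be claimed. It does not remove the mismatch: a distortion that varies with time to next therapy is a further reason to use time at risk. Nor is the window likely to be empty, since AEs are assessed at the End of Treatment visit about 30 days after the last dose (Protocol 11.6), and signs and symptoms accompanying progression are recorded as AEs (Protocol 10.7).

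A reader might go further and infer that AITL and CXCL12+ subjects would look better tolerated than PTCL-NOS subjects. A reader might also take the median PFS values of 50 and 134 days in Protocol 5.2 as about 2 and 5 cycles and derive a spurious 21% excess (1.41/1.16). The documents support neither inference. Those values are PFS, not cycles given. They come from 7 and 8 early subjects split by CXCL12 3'UTR status, not by the SAP subtypes. The 21% also needs h = 1 and the full window in both groups; it falls to 11% at h = 0.5, to 7% if both groups switch at 14 days (1.125/1.05), and to nothing at h = 0.

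It is also fair to say that events per cycle describe drug given, which some readers want, and that this is one descriptive summary among many. Subject-level percentages, laboratory tables by cycle and full AE listings remain. This bears on importance, not on whether the rate is defined consistently.

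**Conclusion.** The point holds in a limited form. As written, the rate combines a numerator that runs to 30 days after the last dose, or to other therapy, with a denominator that stops with the cycles. With the last dose on Day 21, the full window and an equal AE rate throughout, the inflation is 1.82, 1.41, 1.27 and 1.16 at 1, 2, 3 and 5 cycles. It shrinks to 1.00 as the AE rate after the last cycle falls to zero. Early switching or whole-counting of partial cycles can take the factor to 1.00 or below.

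Upward distortion, greatest at few cycles, is the usual direction but not a certain one. Groups with different treatment duration are not comparable on this rate. Which subtype would gain, and by how much, cannot be read from the documents. ORR and the subject-level AE percentages are unaffected, so this is a worthwhile repair to a descriptive table.

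**What to change.** In SAP 9.1, replace the per-cycle definition with TEAEs per patient-month at risk. Sum the denominator over subjects, from first dose to the earliest of last dose plus 30 days, start of other anticancer therapy, death, or last contact. State the month length; SAP 7.3 already uses 30.4375 days.

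If a per-cycle rate is kept, count only events up to the end of the last cycle and count cycles as actual days divided by 28, so that delayed and partial cycles are handled consistently. The SAP should then also say on what date the last cycle ends.

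The cost is one SAP sentence and minor programming, using dates already collected. The drawback is that the new rate is per month at risk and so includes off-drug days in rest weeks, delays and follow-up. The table footnote should say so.

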9.2. Clinical Laboratory Evaluations

The following summary tables will be provided by treatment cycle:

- Incidence of hematological severities Grade 3 or above
- Incidence of chemistry severities Grade 3 or above
- Incidence of blood transfusion or growth factor support

Per subject laboratory results for selected hematology and clinical chemistry will be displayed in listings. Laboratory values outside normal limits will be identified and flags for high and low values along with normal limits will also be presented in these listings.

9.3. Vital Signs

Summary statistics of vital signs and changes of vital signs relative to the assessments at baseline and to the first day of each cycle will be provided

Individual vital sign records will be displayed in Listings.

9.4. ECGs

Summary statistics of ECG Overall Category (Normal, Abnormal Not Clinically Significant, or Abnormal Clinically Significant) will be displayed in a table. Shift of ECG Overall Category from Screening to Cycle 1 Day 1, Cycle 1 Day 7, and End of Treatment will also be provided.

Per subject ECG test results at Screening, Cycle 1 Day 1, Cycle 1 Day 7, repeat assessment and End of Treatment will be displayed in a Listing.

9.5. Other Safety Measures

ECOG performance status per subject during the trial will be displayed in a listing.

10. CLINICAL PHARMACOLOGY ANALYSES

None.

11. OTHER ANALYSES

Not applicable.

12. DATA HANDLING CONVENTIONS

Analyses will be performed using SAS® [SAS Institute 2011] Version 9.3 or higher.

The clinical database will be locked prior to the initiation of the final statistical analyses. A database lock is defined as a stable database that can be analyzed and reported. Changes to a locked database must be authorized in writing by the study sponsor and [REDACTED] standard operating procedures (SOPs).

The data conventions include the following.

- Data will be described and summarized by cohort, according to Protocol Amendment version.
- Summary tables for continuous variables will contain the following statistics: N (number of subjects in the population); n (number of subjects with data for that variable); mean; standard deviation; median; minimum; and maximum. Selected statistics may also include 2 sided 95% normal approximation confidence intervals (CI) on the mean.
- Summary tables for categorical variables will include: N (number of subjects in the denominator); n (number of subjects in the numerator); and percent. Selected statistics also may include a 2-sided 95% CI.
- The baseline value for a given parameter is the last value prior to the first dose. A value is considered to be post-baseline if it is obtained after the first dose. A value is considered to be post-dose on a given cycle day if it is obtained after the dose is administered on that day.
- Data from all study centers will be pooled for all analyses.

- Unless otherwise specified, statistical testing will be 2-sided at a nominal 0.05 level of significance.
- Study day is defined as calendar date – date of first treatment + 1 if the calendar date is on or after the date of first treatment, and calendar date – date of first treatment if the calendar date is before the date of first treatment
- Missing data conventions for individual endpoints are described in the SAP section for the endpoint.
- Listings will be provided for all data collected in the eCRF.

13. REPORTING CONVENTIONS

The table, listing and figure reporting layout will be detailed in the companion document *KO-TIP-002 Table, Listing and Figure Shells*.

14. CHANGES IN THE STATISTICAL METHODS FROM THOSE STATED IN THE PROTOCOL

For the efficacy analysis, the estimation of the objective response rate will be estimated for all subjects in the indicated study population and will not be done separately for each tumor histology type evaluated.

An exploratory Efficacy Analysis (to be performed if results warrant) has been added and is described in Section [8.3](#) of this document.

Summaries for hematology and chemistry-related AEs have been added to the safety analysis.

Laboratory change and shift from baseline will not be performed.

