- 9. Acceptable liver function:
 - a. Bilirubin \leq 1.5 times upper limit of normal (x ULN); does not apply to subjects with Gilbert's syndrome diagnosed according to institutional guidelines.
 - b. AST (SGOT) and ALT (SGPT) \leq 3 x ULN; if liver lymphoma is present, then \leq 5 x ULN is allowed.
- 10. Acceptable renal function with serum creatinine \leq 1.5 x ULN or a calculated creatinine clearance \geq 60 mL/min using the Cockcroft-Gault or MDRD formulas.

11. Acceptable hematologic status:

- a. ANC \geq 1000 cells/ μ L.
- b. Platelet count \geq 50,000/ μ L.
- c. Hemoglobin \geq 8.0 g/dL.

12. Female subjects must be:

- a. Of non-child-bearing potential (surgically sterilized or at least 2 years post-menopausal); or
- b. If of child-bearing potential, subject must use a highly effective method of contraception, such as combined (estrogen and progestogen containing) hormonal contraception associated with inhibition of ovulation, progestogen-only hormonal contraception associated with inhibition of ovulation, intrauterine device, intrauterine hormone-releasing system, bilateral tubal occlusion, vasectomised partner or sexual abstinence. Both females and male subjects with female partners of child-bearing potential must agree to use a highly effective method of contraception for 2 weeks prior to screening, during, and at least 4 weeks after last dose of trial medication. Female subjects must have a negative serum or urine pregnancy test within 72 hours prior to start of trial medication.
- c. Not breast feeding at any time during the study.

13. Written and voluntary informed consent understood, signed and dated.

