10.14.1 Blood Sample Collection for General Clinical Laboratory Assessments

Blood samples will be collected for the following clinical laboratory tests:

- Serum Chemistry: Blood Urea Nitrogen (or Uric Acid), Creatinine, Sodium, Potassium, Calcium, Total Protein, Albumin, Total Bilirubin, Alkaline Phosphatase, ALT, AST, Lactate Dehydrogenase.
- Hematology: White Blood Cell Count, Hemoglobin, Platelet Count, Neutrophils, Lymphocytes, Monocytes
- Coagulation panel: PT/INR, APTT

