12.1.2 Safety Analysis

The All Subjects as Treated (ASaT) population will be used for the analysis of safety data. The ASaT population consists of all enrolled subjects who receive at least one dose of tipifarnib. At least one laboratory or vital sign measurement obtained subsequent to at least one dose of study drug is required for inclusion in the analysis of a specific safety parameter. To assess change from baseline, a baseline measurement is also required.

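### The Grade 3+ laboratory tables take no account of baseline grade and laboratory shift is dropped, so for tests without an entry limit a pre-existing abnormality can be counted as on-treatment toxicity

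*SAP*

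**What the plan says.** **Entry limits.** Protocol 7.1, criterion 11, limits three hematology tests: "ANC \geq 1000 cells" per microliter, "Platelet count \geq 50,000" per microliter and "Hemoglobin \geq 8.0 g/dL". Criterion 9 limits bilirubin and the transaminases. The bilirubin limit "does not apply to subjects with Gilbert's syndrome diagnosed according to institutional guidelines", and the transaminase limit rises from 3 to 5 x ULN with liver lymphoma. Criterion 10 accepts either a creatinine limit or a calculated clearance. Criterion 6 requires recovery to below Grade 2 from acute toxicities, except for Grade 2 toxicities judged not to be a safety risk and toxicity deemed irreversible.

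**Tests collected.** Protocol 10.14.1 lists "Hematology: White Blood Cell Count, Hemoglobin, Platelet Count, Neutrophils, Lymphocytes, Monocytes". Its chemistry panel includes sodium, potassium, calcium, albumin and alkaline phosphatase.

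**Analysis.** SAP 9 gives Grade 3 and 4 hematology results by cycle and across cycles, with similar analyses for chemistry. SAP 9.2 lists, by treatment cycle, "Incidence of hematological severities Grade 3 or above" and the matching chemistry table. SAP 12 defines baseline as the last value before the first dose, but neither laboratory table refers to it. SAP 14 adds that "Laboratory change and shift from baseline will not be performed". SAP 9.3 keeps change from baseline for vital signs, and SAP 9.4 keeps a shift table for ECG.

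**The concern.** A table of laboratory incidence in a single-arm trial is naturally read as what happened on the drug. There is no control group, so each subject's own baseline is the main means of separating drug effect from disease and from lasting effects of prior therapy. If the table ignores baseline, a subject who was at Grade 3 before dosing and stays there is counted in Cycle 1 and in each later cycle, exactly like a new case.

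Safety and tolerability is a secondary objective (Protocol 6.2) and the stated purpose of the 20-subject extension (Protocol 8.1 and 12.4). The adverse event tables cannot fully replace the laboratory tables. Under Protocol 10.4 an abnormal laboratory finding is not reported as an adverse event unless it has signs or symptoms, leads to discontinuation or is judged medically important.

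**Working it through.** The plan states no figure to reproduce. The check compares texts, followed by an illustration of size.

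**Step 1: which tests are exposed.**

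| Test | Entry limit | Can Grade 3+ be present at entry? |
|---|---|---|
| ANC, platelets, hemoglobin | Yes | Largely protected* |
| AST/ALT | Yes, capped at 5 x ULN with liver lymphoma | Largely protected* |
| Creatinine | Limit, or clearance of at least 60 mL/min | Not shown either way |
| Bilirubin | Waived in Gilbert's syndrome | Yes, in those subjects |
| Lymphocytes | None | Yes |
| Total white cells | None, but ANC of at least 1000 implies at least 1000 white cells per microliter | Yes, if Grade 3 extends above that floor |
| Sodium, potassium, calcium, albumin, alkaline phosphatase | None | Yes, where CTCAE grades them |

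*Assumption: Grade 3 starts beyond the entry limit. The documents do not print the CTCAE cut-points. Protection is not complete, because screening laboratory tests may be up to 14 days old.

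Criterion 6 narrows this further. An unrecovered acute toxicity of prior therapy at Grade 3 or above is not admitted unless it is deemed irreversible. What remains is abnormality caused by the disease or judged irreversible.

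**Step 2: does any rule keep such a value out of the table?**

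- Worsening from baseline: SAP 9 and 9.2 have no such condition.
- Timing: Protocol 11.2 places the Cycle 1 Day 1 hematology and chemistry before the first dose (they may be skipped if screening tests fall within 72 hours). The only other scheduled Cycle 1 sample is at Day 7. No text keeps the pre-dose sample out of the Cycle 1 count.
- Onset: the treatment-emergent definition in SAP 9 and the baseline-condition rule in Protocol 10.7 apply to adverse events, not to laboratory grades.
- Separate display: SAP 14 removes shift. What is left is per-subject listings with high and low flags.

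**Step 3: size, by illustration.** Let b be the share of subjects at Grade 3+ at baseline who stay at that grade, and r the rate of new Grade 3+ among the rest. Both are assumed, and all subjects are taken to have baseline and post-dose values.

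- Planned table: b + (1 − b)r
- New onset as a share of all subjects: (1 − b)r
- Difference: b

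With r = 10%:

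| b | Planned table | New onset, all subjects | Difference if N = 70 |
|---|---|---|---|
| 5% | 0.05 + 0.95 × 0.10 = 14.5% | 9.5% | 0.05 × 70 = 3.5 subjects |
| 10% | 0.10 + 0.90 × 0.10 = 19% | 9% | 0.10 × 70 = 7 subjects |
| 20% | 0.20 + 0.80 × 0.10 = 28% | 8% | 0.20 × 70 = 14 subjects |

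**Step 4: how likely is any effect at all?** For one exposed test, with 70 independent subjects, the chance that at least one starts at Grade 3+ is 1 − (1 − b)^70. At b = 2% this is 1 − 0.98^70 = 76%; at b = 5% it is 1 − 0.95^70 = 97%.

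**The case against.** The case against is substantial, and much of it stands.

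- The cytopenias that Protocol 12.2.2 names for the laboratory summary are neutropenia, thrombocytopenia and anemia, and all three have entry limits. This stands. The exposure is confined to the other tests.
- Criterion 6 excludes most unrecovered acute toxicity of earlier treatment. This also stands, so the tables should not be described as broadly mixing in recent prior-therapy effects.
- Protocol 12.1.2 requires a post-dose measurement before a subject enters the analysis of a safety parameter. That rule decides which subjects are included. It does not decide which of their values are counted.
- The current protocol text specifies no laboratory shift table. Protocol 12.1.2 says only that "To assess change from baseline, a baseline measurement is also required". That is correct, though SAP 14 itself lists the omission as a departure from the protocol, and it gives no reason.
- The table shells are a separate document and might include a baseline row. They might, but nothing in the SAP requires one.

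A reader might infer that the Grade 3 or higher rates quoted in Protocol 9.4 for stages 1 and 2, such as leukopenia 50% and lymphopenia 17%, are themselves inflated. The documents do not support this. Those are treatment-emergent adverse event rates, covered by the onset rule and by the rule that stable baseline conditions are not adverse events. A reader might also infer that the transaminase and creatinine allowances admit Grade 3+ values. The first is a capped relaxation and the second an alternative renal test, and the documents show neither to have that effect.

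**Conclusion.** The point holds as a gap in the laboratory-grade tables. For lymphocytes, part of the white-cell range, chemistry tests without an entry limit and bilirubin in Gilbert's syndrome, a Grade 3+ value that predates dosing can be counted as on-treatment incidence, and no planned summary would reveal it. The direction is known: for a given test the planned count can only equal or exceed the count of subjects who worsened. The size is not known, because the documents give no baseline prevalence. The percentages above rest entirely on assumed b and r and on the assumption that baseline abnormality persists at the same grade.

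The documents support saying that pre-existing values can be counted, not that they have been. The summaries are descriptive, and neither the primary endpoint nor the adverse event tables are touched. This is an inexpensive improvement to a secondary-objective safety summary.

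**What to change.** 1. **SAP 14.** Replace the line that drops laboratory shift with a table of baseline CTCAE grade by worst post-dose grade for each graded hematology and chemistry parameter.
2. **SAP 9.2.** Count treatment-emergent Grade 3+ only from values obtained after the first dose of study drug, and only when the grade is worse than the baseline grade. Tie this to the post-baseline definition in SAP 12. The post-dose definition there refers to a given cycle day and would wrongly remove the Day 1 samples of later cycles.
3. **Denominator.** State it as subjects with a baseline value and at least one value after the first dose; for the by-cycle tables, at least one such value in that cycle.
4. **Second column.** Keep the unrestricted Grade 3+ count beside the treatment-emergent one, so that total burden and new onset can both be read.

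No new visit, sample or data field is needed. The cost is SAP wording and a little extra programming.
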